Secondary outcomes and data sources	
Young person outcomes:
 
 1. Internalising score of the Strength and Difficulties Questionnaire (carer report version, internalising score) 2. Prosocial subscale of the Strength and Difficulties Questionnaire (carer report version) 3. Involvement with criminal justice system measured through conviction or subject to youth caution (SSDA903) 4. Transition into residential care (SSDA903) 5. Placement stability measured through unplanned moves (SSDA903) 6. Missing from care (SSDA903) 
Foster carer outcomes:
 
 7. Compassion satisfaction reported by foster carers, measured through the Professional Quality of Life (ProQOL) scale (self-report) 8. Burnout reported by foster carers, measured through the ProQOL scale (self-report) 9. Secondary traumatic stress reported by foster carers, measured through the ProQOL scale (self-report)

	
10. Trauma-informed knowledge reported by foster carers, measured through a bespoke questionnaire (self-report)
 
Supervising social worker and young person’s social worker outcomes:
 
11. Attitudes to trauma-informed practice reported by social workers, measured through the Attitudes Related to Trauma-Informed Care (ARTIC) scale

--	--

SAP version history

Version	Date	Changes made and reason for revision
1.2 [latest]		
1.1		
1.0 [original]		[leave blank for the original version]

Any changes to the design or methods need to be discussed with the YEF Evaluation Manager and the developer team prior to any change(s) being finalised. Describe in the table above any agreed changes made to the evaluation design. Please ensure that these changes are also reflected in the SAP (CONSORT 3b, 6b).

Table of contents

SAP version history	3
Table of contents	4
Introduction	5
Design overview	7
Sample size calculations overview	11
Analysis	15

Introduction

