If, at the analysis stage, the average cluster size proves to be very close to one (that is 1.1 or below) we will use a single-level model rather than two-level. In this case the model will be:

$$Y_{ik} = \beta_0 + \beta_1 Group_{ik} + \beta_2 X_{ik} + \beta_3 LA_k + \varepsilon_{ik} \quad (\text{Eq 2})$$

where

Y_{ik} =externalising score at follow-up for young person i within LA k ;

$\beta_0, \beta_1, \beta_2, \beta_3$ = fixed effect parameters;

$Group_{ik}$ = indicator variable for group allocation of the YP's YPSW and SSW (0=control; 1=intervention) within LA k ;

X_{ik} = baseline externalising score for young person i within LA k ;

LA_k = a vector for the local authority dummy variables, of which there will be seven. β_3 is a coefficient vector for the LA dummy covariates;

ε_{ik} = residual error term.

Secondary outcome analysis

There are a range of secondary outcome measures reflecting the fact that the Theory of Change suggests that impacts should be observed for all the groups potentially affected by the SW training, namely YP, FCs, and the social workers themselves.

1. Young people

There are six secondary outcomes for YP:

- The SDQ internalising score (continuous variable);
- The SDQ prosocial score (continuous variable);

and four outcomes taken from SSSA903 data:

- One or more unplanned moves (binary);

- Transition into residential care (binary);
- Conviction or subject to youth caution (binary);
- Any missing from care episodes (binary).

2. Foster carers

There are four secondary outcomes for foster carers (detailed in the trial protocol):

- The three Professional Quality of Life (ProQOL) subscales (continuous variables):
 - o compassion satisfaction;
 - o burnout;
 - o secondary traumatic stress.
- Knowledge and understanding of TIP score (continuous).

3. Social workers

For social workers in the trial, there is just one secondary outcome:

- ARTIC score (continuous)

The analysis of the secondary outcomes will be conducted following similar overall model specifications as the primary outcome analysis, but with some modifications to reflect the nature of the data. These are:

- The models for the binary outcomes will be logistic regressions rather than linear;
- For the SSDA903 outcomes, for YP just entering foster care there will be no applicable baseline data. To account for this, a baseline outcome will be included in the model coded as categorical: present, absent; not applicable.

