This is a pragmatic trial and it is not possible for the evaluation team to influence the allocation of YPSWs to YPs or the allocation of SSWs to FC, or, of course, the matching of YPs to FCs. An issue that will inevitably arise during the trial relates to the fact that the intervention is being delivered to social workers rather than to the YP themselves. Because YP may change their YPSW, and their FCs may change their SSW, between baseline and follow-up, a control group YP could, during the trial, be re-assigned to a YPSW or SSW who has been trained, and an intervention group YP could be re-assigned to a YPSW or SSW who has not been offered the training¹⁰. These post-randomisation switches are likely to dampen the ITT effect sizes. To test the sensitivity of the ITT estimates to these issues, we will re-run the main

⁹ This is the approach recommended by the What Works for Children's Social Care.

¹⁰ Similarly a YP could move to a new FC with a SSW from the opposite arm of the trial.

two-group analyses per outcome after excluding these switched cases¹¹. Given that the switching is likely to be largely independent of the random allocation – it is more likely to be done by the LA teams for very practical reasons – this should still give close to unbiased estimates, albeit for what may be a non-random subset of YP. However, prior to running this analysis, we will test the assumption that the switching is independent of the random allocation, using a t-test for proportions.

Imbalance at baseline and follow-up

The trial report will summarise baseline characteristics for the two primary arms of the trial for all YP for whom we have baseline data, and separately, for those with both valid baseline and follow-up data. The differences at baseline will provide evidence on whether missing data at baseline (because of baseline non-response by FCs) introduced an imbalance across the arms; the differences at follow-up will provide evidence on whether attrition post-baseline has introduced an imbalance. Note, we do not expect there to be any major imbalances at baseline associated with FC non-response, because the decision taken by a FC on whether or not to take part should be independent of the randomisation. In most cases the baseline data was collected prior to randomisation, but where it was collected post-randomisation, the FC would have been very unlikely to be aware of the allocation of their SSW or their foster child's YPSW.

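### The switched-case re-run for unplanned moves can exclude young people because they had the outcome event

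*SAP*

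**What the plan says.** The passage at issue is in the SAP under Further analyses of the primary trial data, in the subsection on sensitivity to changes of social worker.

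- **Scope.** The plan will re-run the main "two-group analyses per outcome after excluding these switched cases". No outcome is exempted.
- **What counts as a switch.** A control YP counts if re-assigned to a trained worker. On the other side, "an intervention group YP could be re-assigned to a YPSW or SSW who has not been offered the training". Footnote 10, attached to that sentence, adds: "Similarly a YP could move to a new FC with a SSW from the opposite arm of the trial".
- **Justification.** Switching is held to be largely independent of allocation, because "it is more likely to be done by the LA teams for very practical reasons". From this the plan concludes that "this should still give close to unbiased estimates, albeit for what may be a non-random subset of YP".
- **Check.** Before the re-run, the proportions switching are compared between arms. Nothing compares switching with the outcome.
- **The outcome affected.** The summary table lists "Placement stability measured through unplanned moves (SSDA903" among the secondary outcomes. Secondary outcome analysis defines it as "One or more unplanned moves (binary", and says: "The models for the binary outcomes will be logistic regressions rather than linear".
- **A related exception elsewhere.** Under Data collection, YP who leave foster care altogether are excluded from the trial analysis, but the secondary outcomes that capture moves are exempted from that exclusion.

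**The concern.** For most outcomes a change of carer happens during follow-up and is distinct from what is measured. For unplanned moves it may be the measured event. A YP who stays put can be excluded only if a worker is re-assigned. A YP with an unplanned move can be excluded in that way too, and also because the move led to a carer whose SSW is in the other arm. The exclusion therefore depends on the outcome.

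The plan's defence is about dependence on arm. Even if switching were perfectly balanced between arms, the re-run would still remove event cases preferentially. The practical reasons it cites describe caseload re-assignment, not placement breakdown, and RQ2 asks whether the training changes placement stability. At stake is how this one re-run would be read: as a nearly unbiased check on the unplanned-moves result, when it is partly selected on that result.

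**Working it through.** The SAP gives no figure for the effect of this exclusion, so there is none to reproduce.

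**Inputs from the SAP.**
- SSWs at randomisation: 124 intervention, 140 control, 264 in all (Table 2 of the sample size section).
- YP in the two primary arms: 458 intervention, 521 control (sample size section).

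**Assumptions, because the SAP is silent.**
- r is the true unplanned-move rate.
- s is the share of unplanned moves that reach an SSW drawn at random from the trial's SSWs.
- A switch means an SSW in the opposite arm, applied alike to both arms.
- All other switching is ignored.

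**Share of events removed.** This is q = s × (share of SSWs in the opposite arm). With s = 1:
- intervention: qT = 140/264 = 0.530
- control: qC = 124/264 = 0.470

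**Rate left after exclusion.** Of the events, r(1 − q) remain; of everyone, 1 − rq remain. The observed rate is r(1 − q)/(1 − rq). The observed odds are the true odds times (1 − q), so the odds ratio is multiplied by (1 − qT)/(1 − qC), whatever r is.

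**No true effect, r = 20% in both arms (illustrative).**

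| s | qT | qC | Rate left, intervention | Rate left, control | OR |
|---|---|---|---|---|---|
| 100% | 0.530 | 0.470 | 10.5% | 11.7% | 0.89 |
| 75% | 0.398 | 0.352 | 13.1% | 13.9% | 0.93 |
| 50% | 0.265 | 0.235 | 15.5% | 16.1% | 0.96 |
| 25% | 0.133 | 0.117 | 17.8% | 18.1% | 0.98 |

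First row, intervention: 0.20 × 0.470/(1 − 0.20 × 0.530) = 0.0939/0.8939 = 10.5%.

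**Absolute difference.** Suppose half of events are removed in each arm, so the odds ratio is preserved. A true 15% v 10% becomes 0.075/0.925 = 8.1% v 0.050/0.950 = 5.3%. A 5.0-point difference shrinks to 2.8 points.

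**Precision (s = 1, r = 20%, clustering ignored).** Expected events fall from 91.6 to 43.0 (intervention) and from 104.2 to 55.3 (control). Non-events stay at 366.4 and 416.8. The standard error of the log odds ratio is:
- before: √(1/91.6 + 1/366.4 + 1/104.2 + 1/416.8) = 0.160
- after: √(1/43.0 + 1/366.4 + 1/55.3 + 1/416.8) = 0.216

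**Would the planned check notice?** At s = 1 and r = 20%, switching is 0.20 × 0.530 = 10.6% in the intervention arm and 0.20 × 0.470 = 9.4% in the control arm. With 458 and 521 YP, the power to detect this is about 9%. Over r from 5% to 30% it is about 5% to 12%. With equal removal in both arms and no true effect there is no difference to detect, yet exclusion still depends on the outcome.

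**The case against.** The best reply is that this is small and partly acknowledged. It concerns one secondary outcome in one sensitivity re-run, and the plan concedes that the remaining YP may not be a random subset. Footnote 10 reaches only moves to a new carer with an opposite-arm SSW. As worded, it does not catch moves into residential care, to a carer under the same SSW, or to a carer outside the trial. Planned moves to an opposite-arm carer are removed too, as non-events. Even at s = 1 the spurious odds ratio sits well inside the noise: ln(0.886) = −0.121, which is 0.56 of the 0.216 standard error, with an approximate 95% interval of 0.58 to 1.35. All of this limits the size and stands. It does not answer the fault: saying the subset may be non-random does not disclose that it is selected on the endpoint, and the planned check looks only at arm.

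Three stronger readings are tempting, and the SAP does not support them.

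- **That about half of events will be lost.** This is the ceiling at s = 1; nothing in the SAP says where movers go.
- **That the result could be grossly distorted or reversed where allocation was 70%.** Putting 0.70 into the formula gives 0.70/0.30 = 2.33. But 70% is a maximum for allocating YPSWs, most LAs were around 46%, and no LA is reported at 70%. The SSW share can also differ from the YPSW share: in the Appendix illustration, 7 of 14 YPSWs but 4 of 10 SSWs are intervention. The plan fits one pooled model with LA as a fixed effect and makes no LA-specific estimate.
- **That moves to untrained SSWs outside the trial count against the intervention arm only.** The main sentence on switching could be read so. If 20% of moves were of that kind, the null odds ratio would be (1 − 0.624)/(1 − 0.376) = 0.60. But footnote 10, which governs carer moves, speaks of the opposite arm of the trial, and the 20% is an assumption without support in the SAP.

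**Conclusion.** The point holds for unplanned moves. As written, the re-run covers this outcome, and footnote 10 makes some outcome events a ground for exclusion. Independence of switching from allocation would not cure that.

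Under a symmetric opposite-arm rule and the trial's SSW split, a null odds ratio would become 0.89 at the ceiling, 0.96 if half of unplanned moves reach a randomly drawn in-trial SSW, and 0.98 if a quarter do. The lower event rates, smaller absolute differences and lost precision do not depend on the arms differing in the share removed. Actual move rates and destinations are unknown, so none of these figures is a forecast.

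The intention-to-treat estimates, including the one for unplanned moves, and the primary outcome's analysis are untouched. A reader might extend the point to transition into residential care or to the CACE dataset. The SAP does not support that: a move into residential care is not a move to a new foster carer, and CACE is specified for the primary outcome and ARTIC, not for unplanned moves.

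**What to change.** In the subsection on changes of social worker, add one sentence exempting unplanned moves from the switch-exclusion re-run and stating that only the intention-to-treat estimate will be reported for it. This follows the exception already made under Data collection for outcomes that capture moves. The cost is that this one secondary outcome has no switch-sensitivity estimate.

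Alternatively, for this outcome only, count as switched only YP whose YPSW or SSW changed without a placement move. That keeps an estimate, slightly diluted by movers who met an opposite-arm SSW. It needs a derived flag and careful wording. Footnote 11 says the timing of switches will not be known. If the flag simply spares anyone who ever moved, every event case is kept and only YP without an event can be dropped, which selects on the outcome the other way. The exemption is cleaner.

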The analysis of the efficacy trial data will be on an intention-to-treat basis. Estimates of impact per outcome will be based on a multilevel linear regression model with two levels, YPSW and YP, with the baseline version of each outcome being entered as a covariate. LA will be entered as a fixed effect. The analysis will be conducted in SPSS v28.0.1.1 via the MIXED procedure.

If, after non-response, we have data that is essentially unclustered then a single-level model will be fitted.

Primary outcome analysis

The primary outcome measure for YP in the trial is the SDQ externalising score.

The SDQ questionnaire includes five subscales, each with five items, that measure: 1. Emotional symptoms; 2. Conduct problems; 3. Hyperactivity/inattention; 4. Peer problems; 5. Prosocial behaviour. FCs score from 0 to 2 on each item using a scale 'not true', 'somewhat true' or 'certainly true', thus producing a score for each subscale from 0 to 10, where a lower total score is a better outcome for subscales 1-4, and the reverse for subscale 5 (prosocial behaviour). The 'externalising' score (from 0 to 20), is generated by summing the scores of the conduct and hyperactivity subscales.

The calculation of the externalising score will follow the standard SDQ scoring rules. The score will only be calculated where both subscales have a valid score (that is, at least three of the five items have been answered), others being set to missing. Each subscale will be calculated as (total subscale score)*5/(number answered).

The main regression model specification is as follows:

$$Y_{ijk} = \beta_0 + \beta_1 \text{Group}_{jk} + \beta_2 X_{ijk} + \beta_3 LA_k + u_{ijk} + \varepsilon_{ijk} \quad (\text{Eq 1})$$

where

Y_{ijk} = externalising score at follow-up for young person i belonging to assigned at baseline to YPSW j within LA k;

$\beta_0, \beta_1, \beta_2, \beta_3$ = fixed effect parameters;

Group_{jk} = indicator variable for group allocation of the YP's YPSW and SSW (0=control; 1=intervention) within LA k;

X_{ijk} = baseline externalising score for young person i assigned at baseline to YPSW j within LA k;

LA_k = a vector for the local authority dummy variables, of which there will be seven. β_3 is a coefficient vector for the LA dummy covariates;

u_{ij} =random effect for i th member of YPSW j ;

ε_{ijk} = residual error term for i th member of cluster j .

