The characteristics shown will be: YP randomised per LA, gender, age, ethnic group, SDQ externalising mean at baseline, and SDQ internalising and prosocial score means at baseline.

Missing data

We will describe and summarise the extent of missing data per outcome, and the reasons for data being missing where known will be reported on. We will document how much missing data is unit non-response and how much is item non-response, and whether there is evidence for trial imbalance because of missing data either at baseline or follow-up.

The primary ITT regression analysis will be based on complete cases, that is those for which all of the variables needed for the model are complete. The implicit assumption here is that missing data at follow-up is 'missing completely at random' (MCAR). However, because the rate of missing data in this trial is inevitably high (because of non-response to the surveys by FCs either at baseline or follow-up), we will assess the sensitivity of the results to alternative assumptions about the mechanisms leading to missing data.

¹¹ We ruled out analysis that tries to control for these switches because we will not have rich enough data to know when during the trial period the switch occurred, and because of the additional complexity introduced because both or just one of the professionals could be switched

Firstly, we will use the baseline outcome variables for YP and FCs¹², together with other YP and FC characteristics to model (via a logistic regression) the probability per YP of a case being in the intervention arm rather than the control arm. This will identify any observable predictors of imbalance, and the regression model (Eq 1) will be re-run to include, as covariates, any significant predictors that are identified from this logistic regression. This will help establish whether the effect sizes are influenced by the level and nature of missing data, under an assumption of missing at random (MAR).

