Secondly, we will make use of the fact that the SSDA903 data will provide total SDQ scores at baseline and follow-up for many of the young people in the trial, the main exceptions being those young people who have been looked-after continuously for less than 12 months and those aged 17¹³. We will test whether there is evidence of non-response bias in the trial by comparing the mean SSDA903 scores for respondents and non-respondents at each time point, separately within each arm of the trial. If there are observed differences in the means this will allow for an estimate of the magnitude and direction of any bias.

Finally, if there is evidence that outcomes data is missing not at random (MNAR) we will include some estimates of effect sizes based on a range of extreme assumptions about the missing outcomes. This will generate upper and lower bounds for the effect sizes. The assumptions adopted for this sensitivity analysis will include imputing the worst possible outcomes scores for those missing from the intervention arm and the best possible outcomes scores for those missing from the control arm.

The approach will be repeated across all of the secondary outcomes with the probable exception of the SSDA903 outcomes, where we do not anticipate much missing data.

Compliance

Defining 'compliance' for YP in the trial is not straightforward because of the fact that the intervention is being delivered to social workers rather than to the YP themselves, so YP 'compliance' is dependent on the decisions of their YPSWs and SSWs. Because YP may change their YPSW, and their FCs may change their SSW, between baseline and follow-up, compliance

¹² FC baseline data will be used in the model because it is FCs who complete the data about YP.

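### The SSDA903 comparison of respondents with non-respondents does not estimate bias in the treatment effect, although the SAP reads it that way

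*SAP*

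**What the plan says.** All of this is in the SAP.

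- **Missing data, second step.** The aim is stated as "We will test whether there is evidence of non-response bias in the trial". The method is "comparing the mean SSDA903 scores for respondents and non-respondents at each time point, separately within each arm of the trial", using total SDQ from the SSDA903. The reading is "If there are observed differences in the means this will allow for an estimate of the magnitude and direction of any bias". No contrast of the gaps between arms and no adjustment for baseline score is specified.
- **Missing data, final step.** "if there is evidence that outcomes data is missing not at random (MNAR) we will include some estimates of effect sizes" under extreme assumptions, including "imputing the worst possible outcomes scores for those missing from the intervention arm and the best possible outcomes scores for those missing from the control". No criterion for such evidence is given.
- **Missing data, complete-case paragraph.** "The implicit assumption here is that missing data at follow-up is" missing completely at random (MCAR).
- **Primary outcome analysis.** The model is fitted "with the baseline version of each outcome being entered as a covariate", with LA as a fixed effect (Eq 1).

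**The concern.** The quantity the trial reports is the group coefficient in Eq 1. Non-response biases it only if, given baseline score and LA, the relation between response and the follow-up score differs between arms. A raw gap within one arm measures something else: whether responders in that arm have different SDQ scores from non-responders. Where baseline score drives response, or where the gap is much the same in both arms, the gaps are real and the effect is essentially unbiased.

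The MCAR sentence makes a related slip. A complete-case fit of Eq 1 does not need MCAR, because the model already conditions on arm, baseline score and LA.

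This matters because about 60% of the young people in Arms 1 and 2 are expected to be absent from the primary analysis. The SSDA903 is the only planned source that sees the scores of those who did not respond. If its comparison is read as planned, the report may attribute a bias of a stated size and direction to an effect that has none.

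**Working it through.** **1. Inputs from the SAP (Sample size calculations overview).** 979 young people in Arms 1 and 2 (458 intervention, 521 control); 57% with baseline data (558); 70% of those at follow-up (391: 183 and 208); baseline/follow-up correlation 0.6; ICC 0.2; cluster size 1.5. Expected share analysed: 391/979 = 0.40.

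**2. The SAP's own figure.** MDES = 2.80 × √[(1/183 + 1/208) × (1 + 0.5 × 0.2) × (1 − 0.36)] = 0.238, against 0.24 stated. It reproduces and serves here only as a yardstick.

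**3. What a gap implies.** Let g be the mean of respondents minus that of non-respondents in an arm, and p the response rate. The respondents' mean differs from the whole arm's mean by (1 − p)g. The distortion of a between-arm difference is therefore (1 − p₁)g₁ − (1 − p₀)g₀, or about 0.60 × (g₁ − g₀) at 40% response in both arms. Neither gap alone gives it. For Eq 1 the gaps must also be net of baseline score.

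**4. Simulation.** 2,000 trials per scenario, unclustered and without LA effects, 458/521 young people, about 40% response, true effect −0.24 sd. Assumptions not in the SAP: SSDA903 and survey scores correlate 0.8, SSDA903 is complete, response is logistic with the slopes shown per SD, and a gap counts when p < 0.05. The last column is the crude contrast that a reader could form from the raw gaps, put on the survey scale: 0.60 × (g₁ − g₀)/0.8.

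| Response driven by | g₁ (interv.) | g₀ (control) | Either follow-up gap p<0.05 | Eq 1 bias (sd) | Crude contrast (sd) |
|---|---|---|---|---|---|
| Nothing | −0.002 | 0.003 | 11% | −0.005 | −0.004 |
| Baseline, both arms, −0.3 | −0.139 | −0.141 | 54% | −0.001 | 0.002 |
| Baseline, both arms, −0.5 | −0.229 | −0.228 | 90% | 0.001 | −0.001 |
| Baseline, intervention only, −0.5 | −0.223 | −0.002 | 67% | 0.004 | −0.17 |
| Outcome, both arms, −0.5 | −0.383 | −0.378 | 100% | 0.006 | −0.004 |
| Outcome, control only, −0.5 | −0.001 | −0.377 | 99% | 0.18 | 0.28 |

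The Monte Carlo standard error of the bias is about 0.002. Significant gaps are about as common in the third and fifth rows, where Eq 1 is unbiased, as in the last, where it is not. Even the crude contrast is wrong in the fourth row and too large in the last, because it does not remove what baseline explains.

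With weaker baseline-driven response, equal in both arms (log-odds 0.2 to 0.4 per SD, no true effect), Eq 1 bias is 0.00. At least one follow-up gap is significant in 32% to 33% of trials at the lower slope and 76% to 80% at the upper. Counting the baseline comparisons as well, at least one of four is significant in 72% to 99.8%.

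Within the 558 with baseline data, at about 70% response, slopes of −0.3 and −0.5 on baseline give 35% and 67%, again with bias 0.00.

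**5. The direct estimate.** Fit the arm effect on follow-up SSDA903 SDQ, adjusted for baseline SSDA903 SDQ, in everyone and in complete cases, and subtract. Where baseline drove response equally, the difference averaged 0.00. Where gaps ran in opposite directions (+0.13 and −0.12 sd), it averaged 0.15 against a true Eq 1 bias of 0.19. Step 3 agrees: 0.60 × 0.25 = 0.15 on the SSDA903 scale, and 0.15/0.8 = 0.19 on the survey scale.

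**6. The extreme bounds.** Applied only to losses after baseline, 78 of 261 intervention and 89 of 297 control scores are missing (558 split 458:521, less 183 and 208), or 0.30 in each arm. Setting them to 20 and 0 on the 0 to 20 scale moves the difference by about 0.30 × 20 = 6 points, whatever the mean. That is 1.2 to 1.5 sd for an assumed SD of 5 to 4.

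**The case against.** - **Reporting by arm already supplies the contrast.** In part. The four means per time point let a reader compare gaps across arms. But the SAP does not specify that step, and the unadjusted contrast still misleads: with baseline-driven response in the intervention arm only, it is significant in 42% of trials (25% within the 558) while Eq 1 is unbiased.
- **A reader might infer that a raw gap wrongly triggers the bounds.** The SAP writes no such rule. The link is suggested only by the order of the steps and the lack of a criterion. Outcome-driven response equal in both arms is also genuinely missing not at random, so the SAP's condition would then be correctly met although the effect is almost unbiased. The clear misreading is baseline-driven response.
- **A reader might infer that the raw check misses real bias.** Not in general. With opposite gaps it flags 47% of trials against 55% for a baseline-adjusted arm × response term. With outcome-driven response in the control arm only it flags far more (82% against 52% in one set-up, 99% against 57% in another), partly because it lacks specificity. The interaction is too weak to serve as a gate.
- **The percentages are soft.** This stands. Slopes and the 0.8 correlation are assumed. The SSDA903 score lacks those aged 17 or looked after for under 12 months; at an assumed 60% coverage the 31% found in one run at log-odds 0.2 falls to 23%. Some of the absent 60% will have left foster care, and the Data collection section excludes them by design.
- **MCAR is merely conservative.** It is sufficient but stronger than needed. Correcting it changes no analysis, only what the report claims to rely on.

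**Conclusion.** The point holds in limited form. The planned comparison describes whether response is related to SDQ. It does not measure the magnitude or direction of bias in Eq 1's effect, and a raw follow-up gap cannot tell response explained by baseline from data missing not at random. Under the stated assumptions it often shows a gap, in about one third to four fifths of trials, when Eq 1 is unbiased. The exact rates rest on assumed slopes, a 0.8 correlation, complete SSDA903 data and a 5% test that the SAP does not itself specify. The conclusion that the wrong quantity is measured does not depend on them.

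Only sensitivity reporting is affected. The primary estimate is unchanged, and nothing here shows that it is biased.

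**What to change.** 1. Keep the respondent and non-respondent means by arm as description, and drop the statement that they give the size and direction of bias.
2. Among Arm 1 and 2 young people with SSDA903 SDQ at both times, regress follow-up SSDA903 SDQ on arm, baseline SSDA903 SDQ and LA, with Eq 1's clustering. Fit it in all of them and in Eq 1 complete cases. Report the difference in arm coefficients with a 95% CI as the estimated non-response bias. The interval must allow for the overlap of the two samples, for example by resampling YPSWs. Give the arm × response term as support.
3. State the limits: it uses total SDQ as a proxy, excludes those aged 17 or looked after for under 12 months, and is attenuated for externalising. Because the SSDA903 baseline is an imperfect stand-in for the survey baseline, some spurious difference can remain if baseline-driven response differs between arms. State also how those who have left foster care are counted.
4. Do not make the missing-not-at-random analysis depend on the significance of a raw gap or of the interaction. Run it regardless, and use the estimated bias and its CI to inform the range of assumptions alongside the extreme bounds.
5. Replace the MCAR statement with: being a complete case is independent of the follow-up score given arm, baseline score and LA. The label missing at random would be imprecise, because the baseline covariate is itself missing for 43%.

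The cost is SAP wording and a few short regressions on data already being obtained.
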